Thus, COMBI-MB supports the use of dabrafenib and trametinib also in BRAF mutant melanoma patients with brain metastases. However, one of the main critics to this study, is the apparently short progression free survival in the main cohort (cohort A, patients asymptomatic) in comparison with patients treated in other clinical trials with the same combination and no brain metastases: 5.6 months in COMBI MB versus 11 months in COMBI-D. One of the reasons could be the well-known poorer prognosis of these patients, but another one could be the fact that patients in this clinical trial, were not allowed by protocol to be treated with a local therapy (except for previously treated ones in cohort B, C and D, but always before the dabrafenib and trametinib). For those patients achieving a non-complete response, it is unknown if further local therapy (radiation, radiosurgery, surgery) could improve the duration of the responses.

Combination or sequencing of systemic (targeted) and local treatment with radiation has demonstrated a manageable toxicity profile, with some concerns regarding radio necrosis and increase in dermatitis. Most of these data, however, come from retrospective case series.

Finally, although encorafenib in combination with binimetinib is indicated for the treatment of adult patients with unresectable or metastatic melanoma with a BRAF V600 mutation, it is unknown the activity in patients with BRAF mutant melanoma and brain metastases.

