phase. These three first patients, that have achieved non-CR, non-PD in brain and no PD in body, are going to be treated sequentially or at the same time depending on when radiotherapy treatment is needed. If no safety concerns appear (defined as substantial deterioration of vital signs (including ECOG PS), physical examination, ECG, Lab. Values that do not recommend RT), the rest of patients that have achieved non-CR, non-PD in brain will begin local treatment when it will be indicated under medical criteria:

- Encorafenib and binimetinib will be interrupted 24h before radiotherapy and restart 24h after the last dose of radiotherapy.
- The local radiation technique will be defined and indicated by the radiotherapy oncologist (local co-investigator) criteria, depending on the number of lesions and its maximum size in the last tumour assessment done during the treatment with encorafenib and binimetinib:
  - \*Radiosurgery (RS) or Stereotactic radiosurgery (SRS):
    - 1 brain metastases < 4 cm
    - ≤ 3 brain metastases ≤ 3 cm
    - ≤ 4 brain metastases ≤ 2.5 cm

\*Radiosurgery: for patients who do not meet criteria for radiosurgery (RS) or (SRS), exceptional cases could be allowed after prior detailed consultation with the trial coordinators.

- Whole brain radiotherapy (WBRT):
  - ≥ 4 brain metastases
  - Almost one brain metastasis of ≥ 4 cm
  - ≤ 4 brain metastases not eligible for RS or SRS

Location metastases: brain stem, midbrain, pons, medulla or within 10 mm of the optic nerves and chiasm.

- After the first evaluation of the patient's intracranial response, patients without progression who received a local treatment, could receive other local treatments at the discretion of the investigator, if this is considered beneficial for the patient.
- Surgery can be done if, as per investigator criteria, is necessary for the patient's health.
- For patients in CR in the first assessment, if they were not treated with radiation, and in follow up a PD occurs **only in the brain**, brain local treatment will be carried out as per protocol. These patients can continue encorafenib and binimetinib treatment after local treatment.
- Every patient with a stable disease or response in both, brain and body, in the first assessment, when presenting a DP after local treatment in the body CT scan by RECIST 1.1. and/or brain MRI, by modified RECIST 1.1, they will discontinue the systemic treatment with encorafenib and binimetinib.

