# 10.2. Study endpoints

Intracranial objective response (iORR) rate by modified RECIST 1.1 before local treatment in cohort 1 and 2: iORR calculated as the proportion of patient with a best overall intracranial response of complete response (CR) or partial response (PR) before local treatment in cohort 1 and 2. The final statistical analysis of this endpoint is expected to be performed within 3 months after the local treatment of the last patient in any cohort. iORR will be also reported separately for both cohorts.

**Duration of intracranial response in both cohorts (iDOR):** Calculated as the time from the date of first documented CR or PR to the first documented intracranial progression or death due to underlying cancer, in patients with documented intracranial CR or PR before local treatment. The final statistical analysis of this endpoint is expected to be performed within 6 months after database closure expected at 24 months after last patient inclusion, however interim analysis might be performed when analysing other primary variables.

The intracranial progression free survival (iPFS) by modified RECIST in both cohorts: iPFS is defined as the time from the date of inclusion to the date of the first documented intracranial disease progression or death due to any cause, whichever occurs first. PFS will be determined based on tumour assessment (modified RECIST version 1.1 criteria). The local Investigator's assessments will be used for analyses. Those patients who are alive and have not progressed at the last follow-up, date of progression will be censored at the date of the last follow-up. Patient with no additional image test other than baseline will be censored to the day after to inclusion. The final statistical analysis of this endpoint is expected to be performed within 6 months after database closure expected at 24 months after last patient inclusion, however interim analysis might be performed when analysing other primary variables.

Percentage of patients free of intracranial progression at 6 (week 24), 12 (week 48) and 24 months (week 96) in both cohorts: percentage of patients free of intracranial progression assessed by modified RECIST at 6 months (week 24), 12 months (week 48) and 24-month (week 96) considering date of inclusion. The final statistical analysis of this endpoint is expected to be

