# 10.3. Efficacy assessment

Magnetic contrast enhanced brain resonance imaging (MRI) and body CT scan will be performed at baseline and every 8 weeks up to 12 months and according to normal practise thereafter. All lesions selected as target and non-target lesions in the initial evaluation will be measured according to the aforementioned timeline, until disease progression. Imaging tests will be performed using the same method each time.

After local treatment, intracranial lesions (both target and non-target lesions) will be considered as non-evaluable (NE), brain MRI be performed as per protocol (every 8 weeks until first year and according to normal practise thereafter) however disease will be followed only to determine iPFS (unequivocal disease progression or new lesions).

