# 4.6. INTRACRANIAL PROGRESSION-FREE SURVIVAL (IPFS).

Intracranial Progression-free survival (PFS), defined as the time from inclusion (first dose of treatment) until intracranial tumour progression (RECIST 1.1) or death. Patients without any of the previous events are censored at the date of the last available tumor assessment.

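### Further local brain treatment is allowed at the investigator's discretion, but iPFS and iDOR run through it with no stated estimand and no sensitivity analysis

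*Combined protocol and SAP*

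**What the plan says.** **Permission.** Protocol section 5.3, repeated in the Synopsis under Duration of treatment, states that after the first intracranial evaluation "patients without progression who received a local treatment, could receive other local treatments at the discretion of the investigator". It sets no number, timing or trigger. The next bullet reads "Surgery can be done if, as per investigator criteria, is necessary for the patient's health", and this one is not limited to patients without progression.

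**Endpoints.** Protocol 10.2 runs iPFS from inclusion "to the date of the first documented intracranial disease progression or death due to any cause, whichever occurs first", using the local investigator's assessments. For patients alive without progression, "date of progression will be censored at the date of the last follow-up". SAP 4.6 uses the same two events and says "Patients without any of the previous events are censored at the date of the last available tumor assessment". iDOR in 10.2 runs from first response to intracranial progression or death from the cancer, and has no censoring rule.

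**Assessment after local treatment.** Protocol 10.3 makes all intracranial target and non-target lesions non-evaluable. Brain MRI continues every 8 weeks in year 1, but "disease will be followed only to determine iPFS (unequivocal disease progression or new lesions".

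**Analyses by local treatment.** The supplementary SAP tables compare iPFS by radiotherapy (section 2.3) only as yes or no. Nothing separates the planned first course from later ones.

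**The concern.** A patient whose treated lesion grows, but not unequivocally, can be irradiated again or operated on and remain event-free. The person who decides whether growth is unequivocal also decides on re-treatment, in an open-label trial with no central read described. Under section 5.3, progression after local treatment stops both drugs unless the sponsor agrees to continue, whereas re-treatment has no such consequence. Together these give a route by which intracranial events can be delayed.

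At stake is how durability is read. The Trial rationale asks whether local therapy could lengthen responses after BRAF/MEK inhibition. It cites a median PFS of 5.6 months from a dabrafenib–trametinib trial whose patients "were not allowed by protocol to be treated with a local therapy". If iPFS, iDOR and the landmark rates include an unreported number of extra courses, a reader cannot tell whether control came from the drugs plus one planned local treatment or from repeated local treatment.

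**Working it through.** **1. What is and is not touched.** The only planned figure with a sample-size basis is the response rate. The Fleming approximation gives n = [(1.645·√(0.4·0.6) + 0.842·√(0.6·0.4))/0.2]² = 37.1, so 38, and 38/0.8 = 47.5, so 48. Both match protocol 10.1. That endpoint is measured before local treatment, so nothing here alters it. iPFS and iDOR have no planned event count or power, so there is no stated figure to correct.

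**2. Is there a rule for re-treatment?** Setting 5.3 beside 10.2, 10.3, SAP 4.6 and SAP 4.2.1: further local treatment is permitted, and it is neither an event, a censoring reason nor a sensitivity analysis in any of them.

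**3. Illustration of size.** All inputs are assumptions. Intracranial failure is exponential with median 5.6 months, borrowed only as a scale (it is PFS from another trial), so λ = ln 2/5.6 = 0.1238 per month. Without re-treatment, S(6) = 47.6% and S(12) = 22.6%. The share f is 10, 20 or 30%; the documents give no value.

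- *A. Unrelated to failure, no effect.* A share f of patients event-free at month 4 is re-treated and the hazard is unchanged. The median stays at 5.6 months: no inflation.
- *B. Unrelated to failure, halves the hazard.* S(t) = e^(−λt)[(1−f) + f·e^(0.5λ(t−4))] for t > 4.
- *C. Replaces a failure.* A share f of first failures after day 56 (1.84 months) is re-treated instead of being called, with the same hazard afterwards. S(t) = e^(−λt)[1 + fλ(t−1.84)]. At t = 6 the added term is f × 0.1238 × 4.16 = 0.515f.

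| Analysis as planned (re-treatment ignored) | f = 10% | 20% | 30% |
|---|---|---|---|
| B: 6-month rate | 48.2% | 48.8% | 49.5% |
| B: 12-month rate | 24.1% | 25.5% | 27.0% |
| B: median, months | 5.7 | 5.8 | 5.9 |
| C: 6-month rate | 50.0% | 52.5% | 54.9% |
| C: 12-month rate | 25.5% | 28.3% | 31.2% |
| C: median, months | 6.0 | 6.5 | 7.0 |

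C leans high. It lets re-treatment start at day 56, before a first local treatment could have been completed, and it applies f to every later failure, including deaths, which cannot be re-treated.

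**4. How the two sensitivity analyses behave.**

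- *Counting re-treatment as an event.* In C this restores 47.6% and 5.6 months. In A and B it is too low: S(t) = (1−f)e^(−λt) from month 4, so the 6-month rate is 42.8, 38.1 or 33.3% and the median 4.8, 4.0 or 4.0 months.
- *Censoring at re-treatment.* In A and B this restores 47.6%. In C the censoring is informative: S(t) = e^(−λt + fλ(t−1.84)), giving 50.1, 52.7 or 55.5% at 6 months, slightly above the planned analysis.

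Neither version is right in all cases, which is why both are needed and neither should replace the main one.

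**The case against.** The strongest case for the plan is that its definition is coherent. Following patients to progression or death whatever further local treatment they receive is a valid treatment-policy choice, and it suits a trial of a combined strategy. The re-treatment bullet is limited to patients without progression. MRI continues, any new lesion counts, and later documented progression or death is still an iPFS event. A never-irradiated complete responder treated locally for brain-only progression already has an event. The incentive to avoid calling progression is softened because sections 1 and 5.3 let the drugs continue with sponsor agreement. Only untested secondary endpoints are involved.

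All of that stands, and it rules out the stronger reading. A reader might infer that intracranial control is in fact overstated through unlimited salvage. The documents show a route, not an occurrence or a size, and scenario A shows no inflation at all. A reader might also infer that iPFS is to be tested against 5.6 months. The rationale contrasts that figure with a trial in patients without brain metastases, the figure is PFS rather than iPFS, and the only hypothesis (section 4.1) concerns response rate.

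What the objection does not remove is that the treatment-policy choice is nowhere declared, that without progression is judged after local treatment under the non-evaluable rule by the treating investigator, and that the surgery bullet lacks even that limit.

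**Conclusion.** The point holds as a gap in the analysis plan, not as a demonstrated bias. If iPFS, iDOR and the landmark rates are read as describing the drugs plus one planned local treatment, they may be overstated. Read as describing the whole strategy with local treatment as needed, they are sound but unlabelled. On the assumed inputs the shift in the 6-month rate ranges from none to about 7 percentage points (54.9% against 47.6%) and in the median from none to about 1.4 months. These figures depend wholly on how often re-treatment occurs and whether it replaces a failure, neither of which is documented. This is a cheap improvement to secondary endpoints.

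**What to change.** - **Estimand.** In protocol 10.2 and SAP 4.6 and 4.2.1, keep the current definitions as the main analysis and state that further local treatment is handled by treatment policy.
- **Sensitivity analyses.** Pre-specify two for iPFS and iDOR: (a) the first additional brain radiotherapy course or brain surgery given without documented progression counts as an event on its start date; (b) follow-up is censored on that date. Present both beside the main result; conclusions should not rest on (a) alone.
- **Reporting.** Give number, type, date and reason of such treatments by cohort. The Table 47 listing, as shown, has no date or course column, so add both. Surgery can come from the Surgical and Medical Procedures eCRF (7.3.1).
- **iDOR table.** SAP Tables 43–44 give only N, mean, SD, median and range. Add a Kaplan-Meier table, as protocol 10.6 already requires for time-to-event endpoints.
- **Censoring date.** Reconcile last follow-up (protocol) with last tumour assessment (SAP), since (b) needs one rule.
- **Comparison.** Qualify any mention of the 5.6-month PFS: different endpoint, and a trial without local therapy.

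The cost is SAP text, two listing columns, collection of the reason for re-treatment, and re-runs of Kaplan-Meier tables. The downside is that (a) is expected to be lower than the main estimate and understates control when re-treatment was not given for failure, while (b) can fall on either side. No clinical rule changes.

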#### 6. ELIGIBILITY CRITERIA

#### 6.1. Inclusion criteria

Patients eligible for inclusion in this study must meet all the following criteria:

- 1. Written informed consent of approved by the investigator's Institutional Review Board (IRB)/Independent Ethics Committee (IEC), prior to the performance of any trial activities.
- 2. Histologically confirmed diagnosis of unresectable metastatic cutaneous melanoma, or unknown primary melanoma with one or more brain metastasis with a diameter of 5 to 50 mm, measured by contrast enhanced MRI.
- 3. A documented mutation in BRAFV600 in the tumour tissue.
- 4. Modified Barthel Index of Activities of Daily Living > 10 (see appendix 2).
- 5. Subjects aged ≥ 18 years.
- 6. ECOG 0-1 in asymptomatic patients (cohort 1), 0-2 in symptomatic patients (cohort 2).
- 7. Adequate hematologic function:
  - a. Haemoglobin  $\geq$  9 g/dL (may have been transfused).
  - b. Platelet count  $\geq 100 \times 109/L$ .
  - c. Absolute neutrophil count (ANC)  $\geq 1.5 \times 109/L$ .
- 8. Adequate hepatic function defined by a total bilirubin level  $\leq 2.0 \times$  the upper limit of normality (ULN) and AST and ALT levels  $\leq 2.5 \times$  ULN or AST and ALT levels  $\leq 5 \times$  ULN (for subjects with documented metastatic disease to the liver).
- 9. Serum Creatinine  $\leq$  2.0 x ULN or estimated creatinine clearance  $\geq$  30 mL/min according to the Cockcroft-Gault formula (or local institutional standard method).
- 10. Have evidence of at least one measurable lesion as detected by radiological or photographic methods according tto guidelines by modified RECIST 1.1.Patients with unresectable locally advanced or metastatic melanoma untreated or having progressed on or after a prior first line with antiPD1 +/- antiCTLA-4 (patients could have had brain metastasis when treated with immunotherapy). Prior immunotherapy must have ended at least 3 weeks (anti-PD1 monotherapy) or 4 weeks (anti-PD1 + anti-CTLA4) before to the cohort assignment (in case that this premise is not met, please, contact with the sponsor:
- 11. Patients relapsing to a prior adjuvant therapy (e.g. IFN, IL-2 therapy, any other immunotherapy, radiotherapy or chemotherapy) are allowed. When patients received BRAF +/- MEK inhibitors as adjuvant treatment, relapse must have occurred ≥ 12 months after the end of it. Moreover, patient mustn't present any residual grade 3-4 toxicity, including medically serious and reversible/controlled toxicities (e.g.: GGT elevation, CPK elevation, vomiting)

- 12. Steroids or anticonvulsants are allowed if clinically needed and once the patient is included in the trial are not being administered in an increasing dose.
- 13. Female subjects must either be of non-reproductive potential (e.g., post-menopausal by history: ≥60 years old and no menses for ≥1 year without an alternative medical cause; OR history of hysterectomy, OR history of bilateral tubal ligation, OR history of bilateral oophorectomy) or must have a negative urine pregnancy test upon study entry. If the result in the urine pregnancy test is positive, a serum pregnancy test should be done to confirm pregnancy.
- 14. Normal functioning of daily living activities.
- 15. Willingness and ability to attend scheduled visits, follow the treatment schedule and undergo clinical tests and other study procedures.

#### 6.2. Exclusion criteria

Patients meeting any of the following criteria are excluded from the study:

- 1. Uveal or mucosal melanoma.
- 2. History of leptomeningeal metastases, with the exception that they are only seen in brain MRI and the patient has ECOG 0-1 and no neurological symptoms (except for cohort 2, where symptomatic patients will be allowed if ECOG is 0-2).
- 3. Another cancer in the last two years, except for in situ carcinoma of the cervix or squamous cell carcinoma of the skin adequately treated or limited basal cell skin cancer adequately controlled. If another cancer was diagnosed in the two previous years, it should be in complete remission and without the need for any other maintenance treatment (i.e hormonotherapy, chemotherapy, targeted therapy including monoclonal antibodies and immunotherapy)
- 4. History of or current evidence of central serous retinopathy (CSR), retinal vein occlusion (RVO) or history of retinal degenerative disease (RDD).
- 5. Any previous systemic chemotherapy treatment, brain radiotherapy, targeted therapy based on BRAF and/or MEK inhibitors for locally advanced unresectable or metastatic melanoma.
- 6. History of Gilbert's syndrome.
- 7. Previous treatment with a BRAF or MEK inhibitor in metastatic setting. This treatment will be allowed in the adjuvant setting (see above). Previous treatments with immunotherapy will be allowed in both the metastatic and adjuvant setting.
- 8. Known positive serology for human immunodeficiency virus, or an active hepatitis B or hepatitis C infection, or both;
- 9. Impaired cardiovascular function or clinically significant cardiovascular diseases "Clinically significant (i.e., active) cardiovascular disease: cerebrovascular accident/stroke (< 6 months prior to enrolment), myocardial infarction (< 6 months prior to enrolment), unstable angina, congestive heart failure (≥ New York Heart Association Classification Class II), a

- LVEF < 50% evaluated as per institutional guidelines, or serious cardiac arrhythmia requiring medication or a triplicate average baseline QTc interval > 500 ms."
- 10. Uncontrolled arterial hypertension despite medical treatment.
- 11. Moderate (Child Pugh Class B) or severe (Child Pugh Class C) hepatic impairment.
- 12. Impairment of gastrointestinal function.
- 13. Neuromuscular disorders associated with high concentrations of creatine kinase.
- 14. Medical, psychiatric, cognitive or other conditions that may compromise the patient's ability to understand the patient information, give informed consent, comply with the study protocol or complete the study.
- 15. Known hypersensitivity to encorafenib, binimetinib or their components.
- 16. Persisting toxicity related to prior therapy of Grade >1 NCI-CTCAE v 4.03; however, alopecia and sensory neuropathy Grade ≤ 2 is acceptable.
- 17. Female patients who are pregnant or breastfeeding or male or female patients of reproductive potential who are not willing to employ highly effective birth control from screening to 180 days after the last dose of study treatment.
- 18. Known alcohol or drug abuse.
- 19. Inability to swallow tablets or capsules.
- 20. Total lactase deficiency or glucose-galactose malabsorption.

## 7. TREATMENT OF SUBJECTS

## 7.1. Description of Study Drug

#### 7.1.1. Encorafenib

Pharmaceutical form and route of administration: Capsules for oral use.

Strength: provided as 75 mg and 50 mg capsules.

**Presentation:** The encorafenib drug product is supplied as a capsule formulation in dosage strengths of 50 mg and 75 mg the dosage forms for each strength have identical formulations which are packaged into blisters in different coloured capsules per strength. Sites will provide patients enough blisters to cover the treatment until next patient's visit

#### 7.1.2. Binimetinib

Pharmaceutical form and route of administration: Tablets for oral use.

**Strength:** Provided as 15 mg tablets.

**Presentation:** Binimetinib 15 mg will be provided as film-coated tablets and packaged into high-density polyethylene blisters. Sites will provide patients enough bottles to cover the treatment until the next patient visit.

